4.6.8.4. Evaluable Registry Reports

An evaluable registry report is a case with data submitted or confirmed by a HCP that meets the minimum criteria for a registry report, as described in Section 4.1, and for which the pregnancy outcome is known. Pure prospective reported evaluable cases will

be included in the primary study population section of the registry report. Evaluable belimumab exposed traditional prospective and retrospective cases as well as unexposed cases will be summarized separately in the interim and final reports. Participant-reported data without HCP confirmation will also be summarized separately in the final report.

4.6.8.5. Invalid Registry Reports

An invalid case is a report for which the minimum eligibility criteria are never obtained despite requests for the missing data. If the minimum data to determine eligibility are not provided initially, the case will be considered to be pending until all attempts to obtain missing data and requests for follow-up after the initial contact are complete. If after all attempts at follow-up are made, the minimum criteria for registration (detailed in Section 4.1) are still not met, the case will be considered invalid due to insufficient information. Invalid reports will not be included in the registry analyses.

4.6.8.6. Pregnancies in non-SLE Participants

This registry is intended to enroll participants with SLE. If a pregnancy is reported into the registry from a woman who has been exposed to commercially supplied belimumab within the 4 months prior to and / or during pregnancy but she is not diagnosed with SLE, the registry will collect that data. The data from such non–SLE pregnancies will be summarized separately from the pregnancies in participants with SLE. For non-SLE pregnancies, data in the CRF that are relevant to SLE but are irrelevant to the disease for which belimumab was prescribed will not be collected. As such, the data collection for maternal SLE disease severity will not be required for those participants.

4.7. Validation Procedures

Ensuring that the data obtained and delivered to GSK are of high quality will be an ongoing, multi-step process involving programming of edit checks for critical data variables in the data management system and visual review for completeness, logic, consistency, and accuracy. As recommended in regulatory guidance documents, case report forms will be carefully designed to ensure data quality and integrity. Participant-reported data will be verified by the appropriate HCP.

4.8. Endpoints and Data Analysis

This pregnancy registry will be a prospective cohort study and descriptive statistics will be calculated separately for traditional prospective and for pure prospective evaluable data for belimumab exposed participants. Data for belimumab exposed participants will be summarized separately from unexposed patients. In addition, data for participants having SLE will be summarized separately from participants not having SLE.

4.8.1. Belimumab Exposed Participants

The summary statistics for continuous and categorical variables to be used will be specified in the Reporting and Analysis Plan (RAP) but may include means, standard deviations, medians, minimums, maximums, percentiles, and percentages. Frequencies and proportions of adverse pregnancy outcomes, birth defects, and serious and/or

clinically significant infections in infants will be calculated along with their 95% confidence intervals.

The registry data will be used to conduct risk estimation and comparative analyses for the primary endpoint of birth defects and descriptive analyses for all secondary endpoints (i.e. pregnancy and infant outcomes). The presence of a birth defect will be summarized for registry participants with SLE who have been exposed to commercially supplied belimumab within the four months prior to and/or during pregnancy. The birth defect prevalence will be calculated as the percentage of birth defects from the total number of live births [Parker, 2010]; this approach is commonly used in other drug exposure pregnancy registries [Covington, 2004; Tomson, 2004; Holmes, 2008]. Fetal losses occurring at or after 20 gestational weeks with reported birth defects will be included in the estimation for the risk for birth defects to increase sensitivity and to allow comparison of the registry birth defect rates with the CDC MACDP and EUROCAT surveillance systems. An analysis will also be conducted to include fetal losses with reported birth defects for birth defects occurring at less than 20 gestational weeks in the calculation of risk for birth defects.

Analyses will be stratified by subgroups of interest including: timing of exposure (i.e. prior to conception and after conception or during pregnancy as well as trimester or gestational week) and level of exposure (as indicated by dose and duration of belimumab dosing); gestational age at enrollment; maternal age; and region, such as North America and Europe. Additional details on subgroup analyses will be described in the RAP. Comparisons may be made to external cohorts, if appropriate.

Primary Endpoint:

• Birth defects

Secondary Endpoints:

Other pregnancy outcomes

- Spontaneous miscarriage
- Live birth (preterm birth and SGA)
- Stillbirth
- Elective termination

Infant outcomes through age 1 year

• Serious and/or clinically significant infections

4.8.2. Belimumab Analysis Population

The primary study population for which analyses will be presented includes pure prospective evaluable cases in participants having SLE considered exposed to commercially supplied belimumab (Section 4.4) that are not lost to follow-up (i.e., cases with appropriate outcome information that meet the minimum criteria for evaluation as specified in Section 4.1).

While the primary study population is pure prospective reported pregnancies, which can be used to ascertain actual population rates of events, the registry will complement its analyses by comprehensive review of other sources of information about pregnancy outcomes, including traditional prospective and retrospective reports.

4.8.2.1. Exclusions for Analysis Purposes

Invalid cases (Section 4.6.8.5), pregnancies deemed lost to follow-up, retrospective cases, cases where participants do not have SLE, and SLE patients not exposed to belimumab will be excluded from the primary belimumab study population.

4.8.2.2. Analysis Parameters for Birth Defects

Most structural defects originate in the first trimester of pregnancy, the period of organogenesis. Therefore, the outcome data for pure prospective evaluable cases will be stratified by the earliest trimester of exposure to belimumab. For this registry, gestational weeks will be estimated from the most reliable EDD as reported by the HCP. If a CEDD is provided by the HCP, it will be used instead. The date of conception will be calculated as the most reliable EDD minus 38 weeks. If the EDD is not available or never estimated, the first day of the LMP may be used to estimate gestational age. The second trimester begins at week 14 after the date of conception or LMP, and the third trimester begins at week 28.

Only cases meeting the CDC MACDP criteria for a defect or with 2 or more conditional defects will be included in the primary study population. Single minor defects do not constitute a birth defect according to the CDC MACDP classification; therefore, they will be listed in the report, but not included in the primary study population.

The birth defect primary analysis will include pure prospective pregnancies and a sensitivity analysis with traditional prospective pregnancies is planned.

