4. METHODOLOGY

4.1. Study Population

Minimum criteria for enrollment will be the following:

- Exposure classification:
 - For belimumab exposed pregnant women:

Sufficient evidence to confirm that exposure to commercially supplied belimumab occurred within the 4 months prior to and/or during pregnancy ("belimumab exposed")

Or

• For belimumab unexposed pregnant women:

Sufficient evidence to confirm that exposure to belimumab did not occur within 4 months prior to and / or during pregnancy ("unexposed")

• Sufficient information to classify the pregnancy report as prospective or retrospective (Section 4.6.8.1 and Section 4.6.8.2). Retrospective reports of pregnancy are those in which the pregnancy ended before enrollment or at the time of first contact with the registry. Two definitions for prospective reports of pregnancy will be used in this registry, traditional prospective and pure prospective:

Traditional prospective reports of pregnancy will include all women who enroll in the registry before the end of pregnancy (live birth, fetal loss, etc), regardless of known normal or abnormal prenatal test results

Pure prospective reports of pregnancy are a subset of traditional prospective reports and include those where (a) the enrollee did not know at the time of enrollment whether the fetus had a malformation, and (b) no prenatal testing was completed prior to enrollment.

- Full initial reporter (i.e., pregnant woman or HCP) contact information to allow for follow-up (name, address, telephone number/email address) and contact information for applicable HCPs if initial reporter is the pregnant woman
- Consent provided by the pregnant woman for her participation and assent for participation of her infant

Reported cases that do not meet the minimum criteria for registry enrollment will be ineligible for inclusion in the registry and will not be entered into the database. In such cases, the report will be forwarded to GSK and handled using routine pharmacovigilance measures.

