4.6.2. Registration Process

Registry enrollment will be voluntary and may be initiated by pregnant women or by their HCPs, who are acting as data reporters to the registry. After informed consent is obtained from eligible women, the participant and/or her HCPs will complete the *Registration Form* and the initial HCP data collection forms and submit them to the registry. The registry will provide a variety of conventional means for reporters to communicate with and submit data to the registry, including telephone, facsimile, postal mail, and email. The registry will provide a professional contact center in the US and Europe for communication with and collection of data from participants and their HCPs. The registry will also maintain a website that will provide information about the registry to facilitate participant registration and will also provide tools (e.g., down loadable CRF pages) that will facilitate the collection of accurate data.

The following information will be collected at registration.

Reporter Information

- Contact information for the participant as well as two alternate contacts outside the home to include name, address, phone number, and email address. This information will be verified and updated, as needed, at subsequent contacts with the participant.
- HCP reporter contact information

Maternal Information

- Maternal demographics
- Selected maternal medical history
- Previous registry participation
- Previous belimumab clinical trial participation
- Last menstrual period (LMP)
- Estimated date of delivery (EDD) determined from LMP
- Corrected estimated date of delivery (CEDD) (e.g., by ultrasound) if available
- Height
- Pre-pregnancy weight

Maternal Obstetrical History

- Number of previous pregnancies
- Outcome of previous pregnancies: live births, term births, preterm births, stillbirths, neonatal deaths, spontaneous miscarriages, elective terminations, ectopic pregnancies, and molar pregnancies
- History of offspring with birth defects
- Selected maternal conditions in previous pregnancies

• Prenatal imaging and aneuploidy screening/testing performed and findings including the identification of birth defects

Maternal SLE Disease Severity and Health Conditions within the 6 Months Prior to Conception and at Registration

- Baseline confirmation of SLE diagnosis by ACR criteria or clinical diagnosis
- Assessment for accrual of irreversible organ system damage by SDI
- Measurement of SLE disease activity by PGA If available:

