4.6.8. Registry Case Management and Disposition

4.6.8.1. Prospective Registry Reports

The registry will encourage prospective registration, which is defined as those exposures registered before the end of the pregnancy (i.e., live birth, fetal loss, etc). Two definitions for prospective reports of pregnancy will be used in this registry, traditional prospective and pure prospective [Holmes, 2008; Tomson, 2004]. Traditional prospective reports of pregnancy will include all women who enroll in the registry before the end of pregnancy (live birth, fetal loss, etc), regardless of known normal or abnormal prenatal test results. Pure prospective reports of pregnancy are a subset of traditional prospective reports and include those where (a) the enrollee did not know at the time of enrollment whether the fetus had a malformation, and (b) no prenatal testing was completed prior to enrollment. Reports of pregnancy defined as pure prospective will be included in the primary study population. Section 6 addresses the rationale, potential bias, and analytic techniques that may be employed to attempt to control for any known bias that may be introduced by this practice.

Prospective infant follow-up beyond the first year of life will not be routinely solicited by the registry but follow-up may be extended on a case-by-case basis if deemed medically necessary. In addition, while the study remains active, reports of birth defects that were identified in children after the 1st year of life and by 6 years of age will be entered into the database and reported in registry reports. This age criterion is consistent with CDC MACDP practice (see CDC MACDP Case Definition Criteria, 2015). Prospective reports of birth defects in infants beyond the first year of life and by 6 years of age will not be included in the primary study population, but will be described in the text of the registry final report. Prospective reports of infant infections beyond the first year of life will be forwarded to the sponsor for pharmacovigilance purposes only.

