6. STUDY LIMITATIONS

Since participation in the registry will be voluntary, registry participants may not be representative of the overall SLE pregnant population. The most appropriate external comparator data and published literature available may be used to assist the interpretation of pregnancy registry outcome data. Care will be taken during data interpretation since external data may differ from registry data with regard to factors other than belimumab exposure. These factors may include the population under study, SLE clinical characteristics and disease severity, medications used to treat SLE, concomitant medical conditions, data source or collection methods, etc. thus potentially confounding any reported associations. Detailed data on such potential confounders may not be available, especially for any identified external cohorts, and hence it may be difficult to employ adjustment methodologies in the analysis.

The primary study population of belimumab exposed participants will include pure prospective pregnancies (i.e. (a) enrollee did not know at the time of enrollment whether the fetus had a malformation, and (b) no prenatal testing was completed prior to enrollment). Sensitivity analyses will be conducted with traditional prospective pregnancies comprised of women who enroll in the registry prior to the end of pregnancy (live birth, fetal loss, etc), regardless of known normal or abnormal prenatal test results.

While the primary analysis population in this registry will be limited to pure prospective reports, some belimumab-exposed pregnancies will be reported to the registry after the pregnancy ended (i.e. live birth, fetal loss, etc or retrospective reports) or following notification of an abnormal prenatal test result (included in traditional prospective

reports). In general, reports made to the registry after the pregnancy has ended and/or notification of an abnormal prenatal test result are biased toward reporting of the severe and unusual cases and are not reflective of the general experience with the medication. Moreover, information about the total number of exposed persons is not known. Therefore, rates of outcomes cannot be calculated from these data. However, a series of reported birth defects can be evaluated to detect patterns of specific birth defects and can assist with identification of potential early signals of therapy risks.

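### The traditional-prospective sensitivity analysis of birth defects pools women enrolled after an abnormal prenatal result, although Section 6 says rates cannot be calculated from such reports

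*Protocol*

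**What the plan says.** Section 4.8.2.2 fixes the two analysis sets for the primary endpoint: "The birth defect primary analysis will include pure prospective pregnancies and a sensitivity analysis with traditional prospective pregnancies is planned". Section 6 repeats the plan: "Sensitivity analyses will be conducted with traditional prospective pregnancies".

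Sections 4.1 and 4.6.8.1 define the traditional prospective set by enrolment "before the end of pregnancy (live birth, fetal loss, etc), regardless of known normal or abnormal prenatal test results". Pure prospective reports are the subset with no prenatal testing completed and no malformation known at enrolment.

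Section 6 also discusses pregnancies reported "following notification of an abnormal prenatal test result (included in traditional prospective" reports). It says that reports made once the pregnancy is over and/or after "notification of an abnormal prenatal test result are biased toward reporting of the severe and unusual cases and are not reflective of the general experience". It adds that the total number exposed is unknown, and concludes: "Therefore, rates of outcomes cannot be calculated from these data".

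The exclusions in Section 4.8.2.1 apply to the primary population only and do not mention prenatal-test status. The stratification factors named in Section 4.8.1 include gestational age at enrolment but not test status. Section 4.6.2 already collects, at registration, "Prenatal imaging and aneuploidy screening/testing performed and findings including the identification of birth defects".

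**The concern.** Section 6 sets aside one class of report as unusable for rates and, in the same section, plans an analysis of the primary endpoint on a set that contains that class. Nothing in Section 4.8.2.2 or Section 6 says how these reports are handled within the sensitivity analysis.

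The pooled set holds women in three states at entry: untested, tested with nothing abnormal known, and fetal abnormality known. Compared with the untested women, the second group should show a lower defect rate, because detectable defects have been filtered out. The third group should show a higher rate, because some of these women have a known defect and may have registered because of it. Agreement with the pure-prospective result could therefore be two biases cancelling, and disagreement could come from either one. The enrolment target of about 500 is set in traditional prospective pregnancies, so this set is at least as large as the primary one and its estimate may draw attention.

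**Working it through.** **Inputs from the protocol (Section 5).** 500 traditional prospective pregnancies; 83–95% live births; 20–25% lost to follow-up; precision stated for 350 live births at 2.78%, with exact 95% CI (1.32%, 5.09%).

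**Inputs not in the protocol (assumed, shown as ranges).** k, the number of women enrolled with a known qualifying defect; s, the share enrolled after a normal test; d, the share of defects such a test would have found.

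**Step 1: reproduce the plan's figures.** 500 × 0.83 × 0.75 = 311.25 and 500 × 0.95 × 0.80 = 380, as stated. The expected count is 0.0278 × 350 = 9.73. The Clopper–Pearson interval for 9.73 of 350 is (1.325%, 5.093%), which matches apart from rounding of the lower limit.

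**Step 2: upward effect alone.** Rate = (9.73 + k)/(350 + k), with no true excess risk.

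| k (assumed) | Rate | Exact 95% CI |
|---|---|---|
| 0 | 2.78% | 1.33% to 5.09% |
| 3 | 12.73/353 = 3.61% | 1.92% to 6.12% |
| 5 | 14.73/355 = 4.15% | 2.33% to 6.78% |
| 8 | 17.73/358 = 4.95% | 2.95% to 7.74% |
| 10 | 19.73/360 = 5.48% | 3.37% to 8.36% |

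The lower limit first exceeds 2.78% at k = 8 with 350 or 380 live births, and at k = 7 with 311.

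**Step 3: downward effect alone.** The rate among tested-normal women is 0.0278(1 − d)/(1 − 0.0278d), which is 1.96% for d = 0.3 and 1.41% for d = 0.5. If s = 0.4 and the other 60% stay at 2.78%, the pooled rate is 0.6 × 2.78% + 0.4 × 1.96% = 2.45%, or 0.6 × 2.78% + 0.4 × 1.41% = 2.23%.

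**Step 4: both together.** Take s = 0.4 and d = 0.5: 350 × 0.0223 = 7.81 expected cases. Adding k = 2 gives 9.81/352 = 2.79%, almost exactly the background rate although both biases are present. With k = 0 the figure is 2.23%; with k = 5 it is 12.81/355 = 3.61%. The direction of the net error depends on quantities that the protocol does not give.

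**The case against.** The strongest reply is that the main risk is already handled. Traditional prospective cases are kept out of the primary population and summarized separately (Sections 4.6.8.2 and 4.6.8.4), Section 4.8.2 names pure prospective reports as the basis for population rates, and Section 6 discloses the bias. The registry is descriptive and attaches no decision rule to the sensitivity analysis. Subgroup detail is left to the Reporting and Analysis Plan. All of this stands and limits the weight of the point. It does not settle how Section 6 can bar rates from certain reports and also plan an analysis that includes them.

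Several stronger readings are tempting and are not supported:

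- A reader might infer that Section 6 rules out a rate for the whole traditional prospective set. Its bar covers reports made after the pregnancy ended or after an abnormal result. The traditional set also contains every pure prospective case and women with normal tests.
- A reader might infer that the endpoint is already met at entry for these women. The glossary counts screening as prenatal testing, so an abnormal result need not be a qualifying defect under Section 4.3.2. A known defect that ends in elective termination may not reach the numerator either: Section 4.8.4.2 adds fetal losses from 20 weeks, and the glossary's definition of fetal loss does not list elective termination.
- A reader might infer that the pooled rate is bound to be too high. Step 4 shows that it need not be.
- A reader might infer that the pooled rate will be set against MACDP and EUROCAT. Section 4.8.4.2 speaks of registry rates without naming the traditional set.

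It is also fair to object that a rate without the known-abnormality cases is itself biased low, which is unwelcome in a registry meant to detect signals. That is why it should not replace the all-traditional figure.

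**Conclusion.** The point holds as a limited one. As written, the sensitivity analysis pools reports that Section 6 regards as unfit for rates, so Sections 4.8.2.2 and 6 need to be reconciled. The pooled estimate mixes opposing biases and gives little information about the robustness of the primary result. The primary analysis is untouched.

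The possible distortion is not trivial: a handful of known-defect enrolments among about 350 live births would move the estimate by one to three percentage points. That range rests on assumed values of k and on every added woman being an evaluable, counted case. The downward figures rest on assumed s and d. Neither the actual size nor the net direction can be derived from the protocol.

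**What to change.** In Sections 4.8.2.2 and 6, present the traditional prospective birth-defect results by status at enrolment:

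1. no prenatal testing (the pure prospective set);
2. tested, with no fetal abnormality known;
3. fetal abnormality known.

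Give the sensitivity rate for groups 1 and 2 combined, stating that group 2 biases it low. List group 3 separately for signal review. Show the all-traditional figure alongside, labelled as including cases known at entry. State also where a woman with an abnormal screening result but no identified abnormality belongs, because Section 6 speaks of an abnormal result, not of a confirmed malformation.

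The cost is a few sentences and one extra table split. The tests and findings are already recorded at registration, so no new data are needed. The downside is a slightly smaller sensitivity set whose rate is biased low, which is the reason for keeping the all-traditional figure in view.
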